Aim : To compare 2 combination DMARD therapies (MTX+SSZ+HCQ versus MTX+LEF+HCQ) in patient with early RA who have failed MTX monotherapy

Objectives :

1. To assess safety and efficacy of MTX+LEF+HCQ based combination DMARD therapy in patients with early RA failing MTX monotherapy
2. To assess safety and efficacy of MTX+SSZ+HCQ based combination DMARD therapy in patients with early RA failing MTX monotherapy
3. To compare the safety and efficacy profile of 2 combination DMARD therapy (MTX+LEF+HCQ and MTX+SSZ+HCQ)

Methodology

- A. Study design/type:** Randomized parallel group non-inferiority trial, pragmatic design
- B. Study participants:** Humans

For Participants

- a. Inclusion criteria :

Age >18 years satisfying ACR-EULAR criteria for RA

1. Polyarthritis (>4 joints)
2. Disease duration of less than 2 years
3. Patients with moderate to severe disease activity (DAS28 \geq 3.2)
4. Patients who have failed to respond to initial Methotrexate monotherapy

b. Exclusion criteria :

1. End stage disease (deformed fixed joints)
2. Patients with vasculitis, extra-articular features like interstitial lung disease
3. Contraindications to DMARD therapy (Chronic Alcoholism, Chronic liver disease, Evidence of acute/chronic infection, Chronic kidney disease, Patients with leucopenia ($<3.0 \times 10^9/l$), thrombocytopenia ($<150 \times 10^9/l$), AST/ALT $>2 \times$ upper normal value and creatinine clearance <30 ml/minute)
4. Pregnant, lactating women ; patients (both men and women) of reproductive age group unwilling for contraceptive use who have not completed the family
5. Patients unable to come for regular follow up

c. **Number of groups to be studied, their names and definitions:**

Group 1: MTX+LEF+HCQ

Group 2: MTX+SSZ+HCQ

C. Sampling

a. Sampling Population : Patients >18 years of age diagnosed with RA, attending OPD services of the Department of Clinical Immunology

b. Sample size calculation : (calculated for non inferiority trial)

Sample size has been estimated as 70 patients in each group using the N master software considering success rate as 75 % in both groups (calculated from FIN-RACo trial group, Lancet 1999 (13)) and non inferiority limit as 20% with 5 % alpha error ,statistical power of 80 % and dropout rate as 20%

c. Sampling technique: block randomization

D. Randomization details: block of 10, 1:1 random allocation.

E. Study Procedure

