2. Oral low dose Glucocorticoids (GC) - 7.5 mg/d for 4 weeks followed by 5 mg/day for 2 weeks followed by 5mg on alternate day for 2 weeks – as a bridge therapy. Thereafter, it can be given if disease flares (patient being symptomatic with continued DMARD therapy), with the maximum dose being 7.5mg/day.
3. Intra articular steroids-will be allowed during the study, as per severity of patient’s symptoms. The number of intraarticular injections required in each group will be calculated.

DMARD dosages used are:

For all patients as a standard protocol for management of all patients with RA :

1. **MTX** – starting dose 10 mg/week orally for 2 weeks → 15mg / week for 2 weeks 20 mg/ week for 2 weeks → 25mg/ week → assessment of response to MTX after 6 weeks (at the end of 12 weeks after starting MTX)
2. In patients , not tolerating adequate doses of oral MTX in the form of nausea, vomiting, the following strategies will be adopted- 1) dose will be split into two 2) oral MTX will be converted to im formulation.
3. T. Ondansetron 4mg twice a day for 2 days a week will be allowed in the study if patient has nausea or vomiting with MTX.
4. T. Folic acid 5 mg twice a week

Those not achieving adequate response to a maximum permissible dose of MTX (25 mg / week) ie. DAS28ESR >3.2 will be enrolled in the study after randomization:

For **Group 1**

1. T. MTX will be continued at 25mg/week
2. T. folic acid 5 mg twice per week
3. T. LEF -10 mg/day starting dose for 2 weeks → 20mg /day
4. T. HCQ 200 mg/day at night

For **Group 2**

1. T.MTX will be continued at 25mg/week
2. T. Folic acid 5 mg twice a week
3. T.SSZ 500mg once a day for 7 days → 500mg twice a day for 7 days →
500mg thrice a day for 7 days → 1gram twice a day
4. T. HCQ 200mg/day at night

Note: During the course of the study any patients developing extra-articular manifestations requiring different mode of therapy will be excluded from study (but intention to treat analysis will be used for analysis of results).

STATISTICAL ANALYSIS PLAN (SAP)

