The trial is designed as a non-inferiority pragmatic trial. The assessment will be done in unblinded fashion by the researcher. Arbitrarily considering EULAR good response rate (primary endpoint) of 75% with SSZ based triple regimen (tREACH and TICORA study) and non-inferiority margin of $\Delta = (-20\%)$ for LEF, a sample size of 140 (70 in each group) was determined using nMaster sample size calculator (version 2 software) using 2-sided confidence levels (CI) of 95%, power of 80% and dropout rate of 20%.

Data will be analyzed using SPSS (IBM pasw statistics, version 19.0) for windows. For quantitative data [DAS28ESR, iHAQ], normality of distribution will be checked by Shapiro-Wilks W test. Continuous data was presented as median and interquartile range (IQR₂₅₋₇₅) / mean with SD as appropriate. Mann-Whitney U test / Students t test will be used for comparison between median/ mean of 2 groups respectively. Qualitative or categorical variables (such as EULAR good response) will be described as proportions and will be tested using Chi-square. Odds ratio (OR) – odds of achieving the outcome (treatment response) in patients exposed to LEF in comparison to patients not exposed to LEF (SSZ group) along with 95% confidence interval and p-value will be used to study the statistically significant difference in treatment outcome between 2 groups. P-value of <0.05 was considered as significant.

The primary endpoint will be analyzed by both intention-to-treat (ITT) and per-protocol (PP) analysis. The rest of the parameters will be analyzed by ITT analysis only. Patients who do not complete the study, the last observation will be taken as their outcome for ITT analysis. For missing data, the last available readings will be carried forward in case of patients who are not available for the endpoint assessment. Non-inferiority testing will be done by using a 95% confidence interval (CI) of the difference between the proportions of patients achieving the primary endpoint between 2 groups. Extension of CONSORT 2010 statement will be used for reporting of non-inferiority of the LEF group.

DATA COLLECTION PROFORMA

CODE NO:

Date of enrollment:

Name/ age/ sex/ CCR no :

Contact number

Disease duration:

Co-morbid conditions (with duration):

Personal history (habits/addictions):

Treatment history:

Family history:

Baseline Investigations:

RF:

HIV:

HBsAg:

HCV:

Anti-CCP:

Mantoux test:

Drug

Dose

since when

Side effects

1

2

3

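### The 75% response rate behind the sample size has two conflicting bases, and under the SAP's own confidence interval the stated 80% power is about 78% with 70 per group and about 70% with 56

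*Combined protocol and SAP*

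**What the plan says.** The 75% is given in two places.

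- Protocol, C. Sampling, item b (sample size calculation): "considering success rate as 75 % in both groups (calculated from FIN-RACo trial group, Lancet 1999 (13"). The other inputs there are "non inferiority limit as 20% with 5 % alpha error ,statistical power of 80 % and dropout rate as 20"%.
- SAP, first paragraph: "Arbitrarily considering EULAR good response rate (primary endpoint) of 75% with SSZ based triple regimen (tREACH and TICORA study"), with a non-inferiority margin of -20% for LEF, "using 2-sided confidence levels (CI) of 95%, power of 80% and dropout rate of 20"%. The result is that "a sample size of 140 (70 in each group) was determined using nMaster sample size calculator (version 2 software").

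The analysis rule is in the SAP, third paragraph: "Non-inferiority testing will be done by using a 95% confidence interval (CI) of the difference between the proportions of patients achieving the primary endpoint". The primary endpoint is analysed both by intention to treat, with the last observation carried forward, and per protocol. It is EULAR good response at 12 weeks of combination therapy (protocol, section G). Under the DMARD dosages heading, the patients randomised are described as "Those not achieving adequate response to a maximum permissible dose of MTX (25 mg / week").

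**The concern.** The 75% does two jobs. It sets the variance behind the sample size and so the power, and it alone gives the fixed 20-point margin a relative meaning. One section says the figure was calculated from one trial. The other calls it arbitrary and names two different studies. A reader cannot tell which account is right, or whether the figure fits patients who still have active disease after 12 weeks of methotrexate and are assessed 12 weeks later. Neither section gives a rationale for the margin or shows how power changes with the control rate.

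At stake is how a result is read. A confidence interval that crosses -20 points would be judged against a promised 80% power that the planned analysis does not have. A pass would be judged against a margin whose severity depends on an unsettled control rate.

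**Working it through.** **The two statements side by side**

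| | Protocol, C.b | SAP, first paragraph |
|---|---|---|
| Value | 75%, both groups | 75%, SSZ regimen |
| Named source | FIN-RACo | tREACH and TICORA |
| Status | calculated | arbitrary |
| Outcome wording | success rate | EULAR good response (primary endpoint) |
| Tied to methotrexate failures at 12 weeks | not shown | not shown |

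**Inputs.** True rate p = 0.75 in both arms; margin 0.20; power 80%; dropout 20%; 70 per group (both sections). Allocation is 1:1 (protocol, section D). The interval is two-sided 95%, which is one-sided 2.5% for non-inferiority (SAP).

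**Step 1: reproduce 70 per group.** n = (z_alpha + z_beta)² × 2p(1-p) / margin², with 2p(1-p) = 0.375 and margin² = 0.04.

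- One-sided 5%: (1.645 + 0.842)² × 0.375 / 0.04 = 57.96, so 58. Then 58 × 1.2 = 69.6, so 70. This matches the plan.
- One-sided 2.5% (the SAP's interval): (1.960 + 0.842)² × 0.375 / 0.04 = 73.6, so 74 evaluable. Then 74 × 1.2 = 89, or 74 / 0.8 = 93. Neither is 70.

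Of the combinations tried, only one-sided 5% with n × 1.2 gives 70. The SAP's two-sided 95% interval does not.

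**Step 2: power of the planned analysis at 75%.** After 20% dropout, 70 × 0.8 = 56 per group. Power ≈ Φ(0.20 / SE - 1.960), with SE = √(2p(1-p)/n).

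- n = 70: SE = √(0.375/70) = 0.0732; 0.20/0.0732 = 2.733; Φ(0.773) = 78.0%.
- n = 56: SE = √(0.375/56) = 0.0818; 0.20/0.0818 = 2.444; Φ(0.484) = 68.6%.

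Exact enumeration of two binomials with a Wald 95% interval gives 78.4% and 69.6%.

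**Step 3: other control rates.** The documents give none, so every rate below 75% is an assumption. Equal true rates in both arms, exact enumeration, and the share of control response the margin lets LEF lose (0.20/p):

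| Assumed rate | Power, 70 per group | Power, 56 per group | Permitted relative loss |
|---|---|---|---|
| 75% | 78.4% | 69.6% | 27% |
| 60% | 67.2% | 58.4% | 33% |
| 50% | 66.4% | 54.2% | 40% |
| 40% | 67.2% | 58.4% | 50% |
| 30% | 73.8% | 64.5% | 67% |
| 20% | 84.3% | 75.9% | 100% |

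Power is lowest at 50% and recovers below it, because the variance p(1-p) is symmetric about one half. The permitted relative loss rises throughout.

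**Step 4: chance of passing if LEF has half the SSZ response** (70 per group, same method): about 0% at 75% v 37.5%, 2.5% at 40% v 20%, 11% at 30% v 15%, and 39% at 20% v 10%.

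**The case against.** The two sections agree on 75%, the 20-point margin, 80% power, 20% dropout and 70 per group, so the discrepancy in citation and status changes no planned number. The SAP does tie 75% to the SSZ triple regimen and to the primary endpoint; only the population and timing are left open. The protocol's generic term for success need not mean a different outcome. A fixed absolute margin tested on a risk difference is an ordinary choice. The SAP also plans group proportions and an odds ratio with its interval, so a low SSZ rate would be visible to readers. All of this stands. It limits the point but does not remove the conflict over source and status, or the gap between 80% and the power of the planned interval at 75% itself.

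Three stronger readings are tempting, and the documents do not support them.

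- That 75% is too high. No document gives a lower SSZ rate, and the cited trials cannot be checked from here.
- That power falls steadily as the SSZ rate falls. It does not: it is 84% at 20% with 70 per group.
- That the margin would readily pass a much worse regimen. At 40% v 20% the chance is the nominal 2.5%. It becomes material only at assumed rates of about 30% or below, less than half the planned rate.

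A reader might also want a second pass criterion on the odds ratio when the SSZ rate is low. The odds-ratio equivalent of the margin, (0.55/0.45)/(0.75/0.25) = 0.41, is built from the same disputed 75% and 20 points. Any observed-rate trigger, such as 40%, would be an outside choice that depends on the data. With that trigger and limit, power at a 20% rate would fall from 84% to 58%. I would not add it.

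**Conclusion.** The point holds in this form. The protocol and the SAP conflict on where the 75% comes from and on whether it was calculated or assumed, and neither shows that it fits methotrexate failures at 12 weeks.

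The stated 80% is also wrong for the planned analysis on the plan's own inputs. The shortfall is about 2 points if all 70 per group are analysed, as under intention to treat with carried-forward values. It is about 10 points with 56 evaluable per group, which is closer to the per-protocol position if the planned 20% dropout occurs. These two figures need no outside rate. They assume equal true rates of 75% and a Wald interval; the SAP does not name the interval method.

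The further fall, to 66-67% (70 per group) and 54-58% (56 per group), holds only if the true rate is 40% to 60%, which is an assumption.

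**What to change.** 1. In protocol C.b and the SAP's first paragraph, give the same single basis for 75%. If it was derived, name the source and show how the figure follows for this endpoint, time point and population. If it is an assumption, label it so in both places and remove the claim that it was calculated.
2. Replace the single 80% with power under the two-sided 95% interval at 70 and 56 per group, over assumed SSZ rates of, for example, 20% to 75%. The table above can be used directly.
3. Beside it, state what the fixed 20-point margin permits LEF to lose: 27% of the control response at 75%, 50% at 40% and 67% at 30%. Give the clinical reason for accepting 20 points.

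The cost is wording in two sections, with no added patients, visits or procedures and no change to the decision rule. The price is that the stated power becomes a less favourable range.

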A. Selection of participants: All consecutive patients of RA attending the OPD services of the department of Clinical Immunology will be included to reach a minimum sample size of in each group.

[figure not shown]
B. Patients will be assessed for eligibility and will be started on Methotrexate monotherapy initially and then only patients, who have moderate to severe disease activity inspite of 12 weeks of Methotrexate monotherapy, will be randomized to either of the 2 groups of DMARDs.

C. Allocation to groups:

Allocation concealment will be done by : Sequentially numbered, opaque, sealed envelopes (SNOSE) method

Group 1: MTX+LEF+HCQ

Group 2: MTX+SSZ+HCQ

F. Data Collection method including settings and periodicity: Patients aged above 18 years diagnosed as RA according to the 2010ACR-EULAR criteria will be screened and evaluated for inclusion in the study. The patients will be examined every 2 week interval during DMARD dose escalation & then every month for next 6 weeks of MTX and for 24 weeks for either groups.

a. Clinical evaluation:

- i. Adverse drug reactions (ADRs) – each visit
- ii. IHAQ, DAS28 - once at baseline and then at 12 weeks of MTX monotherapy and then at the end of 24 weeks treatment with either of Group 1 or group 2 drug.

b. Laboratory:

- i. Routine CBC/RFT/LFT: every 2 week interval during dose escalation & then every month for 12 weeks after starting the drug
- ii. ESR & hsCRP for disease activity evaluation: every month.
- iii. **USG** wrist, hand and feet (US-7 score)- at baseline and at 12 weeks of Group 1 or group 2 drug

G. List of variables and their measurement methods with standardization techniques:

a. (i) Independent variables

Socio-demographic profile:

- Age
- Gender

b. Outcome Variables:

Disease-related parameters –

Primary outcome measures:

- a. Disease activity (state) - DAS28

Secondary outcome measures:

- a. Functional ability – iHAQ
- b. Mean changes over time in:
 - i. Inflammatory parameters: ESR, hs-CRP
 - ii. Disease activity as per US-7 score
- c. Adverse drug reactions

Primary endpoint:

Proportion of patients in both groups achieving good response according to European League Against Rheumatism (EULAR) response criteria at the end of 12 weeks of combination therapy

Secondary endpoint:

1. Change in functional ability (Indian Health Assessment Questionnaire; iHAQ) at the end of 12 weeks of combination therapy
2. disease activity by US7 score at 12 weeks

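### With a two-sided 95% CI, 70 per group does not give the stated 80% power: 74 evaluable (about 93 randomised) per group are needed, and 70 gives about 69% to 78%

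*Combined protocol and SAP*

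**What the plan says.** The sample size is justified in two places.

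- **Protocol, C.b Sample size calculation:** "Sample size has been estimated as 70 patients in each group using the N master software considering success rate as 75 % in both groups", with "non inferiority limit as 20% with 5 % alpha error ,statistical power of 80 % and dropout rate as 20" per cent. Whether the 5% is one-sided or two-sided is not stated.
- **SAP, first paragraph:** the same 70 per group (140 in total), from a 75% good-response rate with the SSZ regimen and a margin of −20% for LEF, "using 2-sided confidence levels (CI) of 95%, power of 80% and dropout rate of 20" per cent.

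The SAP's third paragraph gives the test that will be run: "Non-inferiority testing will be done by using a 95% confidence interval (CI) of the difference between the proportions of patients" achieving the primary endpoint. On analysis sets it says: "The primary endpoint will be analyzed by both intention-to-treat (ITT) and per-protocol (PP) analysis". On missing data it says: "For missing data, the last available readings will be carried forward in case of patients who are not available for the endpoint assessment". The primary endpoint is good response by EULAR "response criteria at the end of 12 weeks of combination therapy", while follow-up runs to 24 weeks.

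**The concern.** A non-inferiority claim based on a two-sided 95% CI is a one-sided test at 2.5%. At that level the stated inputs call for more than 70 patients per group before any dropout is added, yet the 70 is presented as already including 20% dropout. The stated 80% power and the stated sample size therefore cannot both be right.

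What is at stake is the chance of an inconclusive trial. If LEF really is as good as SSZ, the plan tells its readers that non-inferiority will be missed in 20% of such trials. The true figure is higher, and most clearly so in the per-protocol analysis, which the SAP runs on the primary endpoint alongside ITT.

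**Working it through.** **Inputs**

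- Response 75% in each group, so the expected difference is 0 (protocol C.b; the SAP paragraph gives 75% for SSZ only)
- Margin 20 points (both places)
- Two-sided 95% CI, i.e. one-sided 2.5%, z = 1.960 (SAP, first and third paragraphs)
- Power 80%, z = 0.8416; dropout 20% (both places)
- 1:1 allocation (protocol, D. Randomization details)

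**Where 70 could come from**

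Per-group size: n = (z_alpha + z_power)² × 2 × 0.75 × 0.25 / 0.20².

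With one-sided 5% (z = 1.645): n = (1.645 + 0.8416)² × 0.375 / 0.04 = 57.96, so 58. Multiplying by 1.2 gives 69.6, so 70. This matches, but it is an inference: the documents state neither a one-sided 5% test nor an inflation formula. The usual inflation gives 58 / 0.8 = 72.5, so 73.

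**The size from the stated inputs**

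With z = 1.960: n = (1.960 + 0.8416)² × 0.375 / 0.04 = 73.58, so **74 evaluable per group**.

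- Inflated as n/(1 − 0.20): 74 / 0.8 = 92.5, so **93 randomised per group** (73.58 / 0.8 = 92 if not rounded first).
- Inflated as n × 1.2: 74 × 1.2 = 88.8, so 89.
- Variants: the Farrington-Manning method also gives 74 (93 after dropout); a continuity correction gives 84 (105 after dropout).

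No variant tried at the two-sided 95% level gives 70 after dropout, and 70 is already below 74 before dropout.

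**Power with 70 randomised per group, per-protocol set**

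Power = Φ(0.20 / √(0.375/n) − 1.960). For n = 56: √(0.375/56) = 0.0818; 0.20 / 0.0818 = 2.444; Φ(0.484) = 0.686. The documents do not say how much of the 20% dropout falls before week 12, so the range is shown.

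| Lost before week 12 | Evaluable per group | Power |
|---|---|---|
| 0% | 70 | 78.0% |
| 5% | 66.5 | 75.9% |
| 10% | 63 | 73.6% |
| 15% | 59.5 | 71.2% |
| 20% | 56 | 68.6% |

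For comparison, n = 74 gives 80.2%.

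Exact binomial calculation gives slightly higher values: 78.4% (n = 70) and 69.6% (n = 56) with a Wald interval, and 79.3% and 70.4% with a Newcombe interval. All are below 80%.

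**Power in the ITT set, all 70 analysed**

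Take 56 completers responding at 75% and 14 dropouts per group whose last value is carried forward. The dropouts' response rate q is an assumption, because the documents give none. Responders per group are Bin(56, 0.75) + Bin(14, q); power is by exact enumeration with the Wald interval.

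| q | Overall response | Power |
|---|---|---|
| 75% | 75% | 78.4% |
| 50% | 70% | 74.3% |
| 25% | 65% | 71.6% |
| 0% | 60% | 71.0% |

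**The case against.** The strongest reply has four parts.

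- **The loss may be small.** With all 70 per group in the ITT analysis at 75% response, power is 78.0%, or 79.3% with the Newcombe interval. Type I error, margin, endpoint and decision rule are all untouched. This is fair, and it is why the conclusion is given as a range. Even this best case is below 80%, and it leaves no allowance for the dropout that the plan itself expects.
- **The 69% is conditional.** It needs the whole 20% to be lost before week 12, although follow-up lasts 24 weeks. That stands. In the other direction, the documents do not define the per-protocol set, so protocol deviations could take it below 56.
- **C.b alone is not wrong.** Its 5% alpha has no stated sidedness, and 70 can be reached from one-sided 5%. That stands too: C.b does not contradict the SAP's interval. It does not help the SAP paragraph, which attributes 70 to a two-sided 95% CI, the same confidence level that the SAP's test uses.
- **The lower ITT figures change the planning rate.** Carried-forward response below 75% lowers overall response below the planned 75%. Those rows are a sensitivity analysis on assumed rates and do not follow from the plan's inputs. The shortfall does not depend on them.

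**Conclusion.** The SAP's sample-size statement is wrong as written. At 75% in both groups, a 20-point margin and a two-sided 95% CI, 80% power needs 74 evaluable and about 93 randomised per group. The plan has 70. By the normal approximation, power with 70 randomised runs from 68.6% (56 evaluable per group) to 78.0% (all 70 analysed at 75% response). It is below 80% at every dropout timing and with each interval method checked.

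If the two regimens are truly equal at 75%, non-inferiority would be missed in about 31% of trials at 56 evaluable and about 22% at 70. The plan implies 20% after dropout. There is no added risk of a false non-inferiority claim, since the planned 95% CI is stricter than the one-sided 5% test that would explain the 70.

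The conclusion rests on C.b's equal 75% rates. The software's internal formula is not given, but the stated inputs are enough to test the stated result.

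**What to change.** Change the wording in both C.b and the SAP's first paragraph:

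1. State alpha as one-sided 2.5%, applied through the lower limit of the two-sided 95% CI for LEF minus SSZ.
2. State the dropout inflation as n/(1 − 0.20).
3. Replace the 80% power claim with text such as: *With 70 randomised per group and 75% response in both, power is about 69% in the per-protocol set if 20% are lost before week 12 (56 evaluable), and up to about 78% in the ITT set (all 70 analysed, assuming carried-forward dropouts also respond at 75%; about 71–74% if 0–50% of them respond). Power of 80% would need 74 evaluable, about 93 randomised, per group.*

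The cost is two reworded paragraphs and a less favourable stated power. No patients are added, and the margin, endpoint and test stay as they are. Keeping the 80% claim would instead mean randomising about 93 per group: 186 in total, 46 more than the planned 140.

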| | Baseline | 4mo | 5mo | 6mo |
|---------------|-----------------|------------|------------|------------|
| IA Steroids | | | | |
| Oral steroids | | | | |

| | Baseline | 4 week | 8 week | 12 week | 16 week | 20 week | 24 week |
|--------------------------|-----------------|---------------|---------------|----------------|----------------|----------------|----------------|
| TJ28 | | | | | | | |
| SJ28 | | | | | | | |
| VAS | | | | | | | |
| ESR | | | | | | | |
| hsCRP | | | | | | | |
| DAS28 | | | | | | | |
| iHAQ | | | | | | | |
| Morning stiffness | | | | | | | |

| | | | | | | | |
|--------------------------------|--|--|--|--|--|--|--|
| Extraarticular features | | | | | | | |
| Adverse drug reactions | | | | | | | |

FOLLOW UP INVESTIGATIONS

| Investigations | Baseline | 4W | 8W | 12W | 16W | 20W | 24W |
|-----------------------|-----------------|-----------|-----------|------------|------------|------------|------------|
| Hb | | | | | | | |
| TLC | | | | | | | |
| DLC | | | | | | | |
| MCV | | | | | | | |
| Platelets | | | | | | | |
| Peripheral smear | | | | | | | |
| Urine albumin | | | | | | | |
| Microscopy | | | | | | | |
| Blood urea | | | | | | | |
| Sr. Creatinine | | | | | | | |
| Bilirubin (T/D) | | | | | | | |
| AST/ ALT | | | | | | | |
| ALP/GGT | | | | | | | |
| Total protein /Alb | | | | | | | |
| CPK / LDH | | | | | | | |
| Sugar (AC/PC) | | | | | | | |
| CH/TG/HDL/LDL | | | | | | | |
| CT/USG/MRI | | | | | | | |
| ECG/ECHO | | | | | | | |

| US7 Score | | Baseline | 12 week | 24 week |
|------------------|-----------|-----------------|----------------|----------------|
| Synovitis | GS | | | |
| | PD | | | |
| TS | GS | | | |
| | PD | | | |
| Erosion | GS | | | |

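### Monthly ESR and hsCRP are declared as changes over time, but the SAP names no visit, no contrast and no baseline adjustment for them (free improvement, low severity)

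*Combined protocol and SAP*

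**What the plan says.** The protocol's list of secondary outcome measures (section G.b) has the entry "Mean changes over time in", and under it "Inflammatory parameters: ESR, hs-CRP". The laboratory schedule (section F.b) has "ESR & hsCRP for disease activity evaluation: every month". The data collection proforma has rows for both markers at baseline and then at "4 week | 8 week | 12 week | 16 week | 20 week | 24 week".

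The numbered secondary endpoints that follow do not mention either marker. The other item under the same entry, the US-7 score, does reappear there with a time point (12 weeks), as does iHAQ.

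The SAP (second paragraph) introduces continuous data with "For quantitative data [DAS28ESR, iHAQ], normality of distribution will be checked by Shapiro-Wilks W test". ESR and hsCRP are not in that bracketed list as outcomes of their own. The only comparison given for continuous data is "Mann-Whitney U test / Students t test will be used for comparison between median/ mean of 2 groups respectively", followed by "P-value of <0.05 was considered as significant". The third paragraph adds "The rest of the parameters will be analyzed by ITT analysis only" and fills missing endpoint readings by carrying the last one forward. There is no baseline covariate, repeated-measures model, summary measure or multiplicity rule.

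**The concern.** A declared secondary outcome has up to six follow-up readings per patient, and the plan does not say which reading, or which summary of them, will be compared between arms. That leaves the number of tests and the choice of visit open until the data are in hand. It also leaves baseline adjustment out, although the baseline readings are already collected.

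This matters somewhat more for these two markers than for other secondary measures. The SAP says that assessment is unblinded and by the researcher, and the protocol says the same of ultrasound. ESR and hsCRP are the only stand-alone efficacy measures that are read by the laboratory, so readers are likely to look to them for support of the unblinded clinical result. Support of that kind is weak if the visit could have been picked afterwards.

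**Working it through.** The documents give no figure for the ESR and hsCRP analysis, so there is none to reproduce. The stated 70 per group belongs to the primary endpoint.

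**Inputs from the documents.** 2 markers (G.b); 6 follow-up columns (proforma); 0.05 per test, no multiplicity rule (SAP); two-group t or Mann-Whitney test (SAP).

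**Assumptions.** The documents give no SD or correlation. I take a within-patient correlation r between visits, baseline included, of 0.3, 0.5 and 0.7, equal for all pairs of visits, and a cross-marker correlation of 0.4 at the same visit. The arms do not truly differ.

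**1. How many tests the wording allows.** Fewest: one change score per marker, 2 × 1 = 2. Most: every form visit, 2 × 6 = 12.

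**2. Chance of at least one false positive.** If tests were independent this is 1 − 0.95^k: 9.75% for k = 2, 26.5% for k = 6, 46.0% for k = 12. These are ceilings, because the readings are correlated. Simulating correlated normal test statistics, two-sided 5% each, with the cross-marker correlation at different visits taken as 0.4 × r:

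| Reading of the SAP | Tests | r = 0.3 | r = 0.5 | r = 0.7 |
|---|---|---|---|---|
| One change score per marker | 2 | 9% | 9% | 9% |
| Weeks 12 and 24 only | 4 | 17% | 17% | 15% |
| Three visits | 6 | 24% | 22% | 20% |
| All six visits | 12 | 41% | 36% | 29% |

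If the cross-marker correlation is instead 0.4 between all pairs of visits, the last row becomes 37%, 34% and 28%. Hence the range of about 28% to 41%.

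**3. Baseline adjustment at one visit.** Take the variance of a raw-value comparison as 1. A change score has variance 2(1 − r), and ANCOVA on baseline has 1 − r².

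| r | Raw | Change | ANCOVA | SE, ANCOVA / raw | SE, ANCOVA / change |
|---|---|---|---|---|---|
| 0.3 | 1 | 1.40 | 0.91 | √0.91 = 0.95 | √(0.91/1.40) = 0.81 |
| 0.5 | 1 | 1.00 | 0.75 | √0.75 = 0.87 | √(0.75/1.00) = 0.87 |
| 0.7 | 1 | 0.60 | 0.51 | √0.51 = 0.71 | √(0.51/0.60) = 0.92 |

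So the SE falls by 5% to 29% against a raw-value test and by 8% to 19% against a change-score test.

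**4. Averaging visits.** The baseline-adjusted mean of weeks 4, 8 and 12 has variance (1 + 2r)/3 − r² = 0.443, 0.417 and 0.310. Its SE is √(0.443/0.91) = 0.70, √(0.417/0.75) = 0.75 and √(0.310/0.51) = 0.78 of the single-visit ANCOVA. This estimates an average over the window, not the effect at week 12. The window includes the dose steps of LEF and SSZ, and may overlap the 8 weeks (4 + 2 + 2) of bridging glucocorticoid that the protocol allows.

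**The case against.** The strongest case on the other side is that this is only a missing line of specification, and that several tempting readings go beyond the documents. Most of that stands.

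- A reader might infer that every marker will be tested at every visit. The SAP does not say so. Monthly collection is not a plan for monthly testing, and the rule that a non-completer's last observation becomes the outcome points, if anything, to one value per patient. The 12 tests are an upper bound.
- A reader might infer that a two-group test cannot address change over time. It can: a t or Mann-Whitney test on each patient's change from baseline compares change between arms and fits the SAP's wording.
- A reader might set 28% to 41% against 5%. One contrast per marker is still two tests, so the fair comparator is about 9% unless alpha is split.
- A reader might claim the gain from averaging visits as pure precision. It belongs to a different estimand, in which early differences between arms could be smaller.
- A reader might call these the trial's only laboratory-read efficacy data. ESR is also a component of DAS28ESR, so the statement holds only for stand-alone measures.

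The count of six post-randomisation visits is also not quite settled. The steroid table on the same form is headed in months 4 to 6, so its clock may start with methotrexate monotherapy. Against that, the protocol reassesses response 12 and 24 weeks after allocation, and a form counted from the start of methotrexate would have no column for the later of these. If only three visits follow randomisation, the upper bound is 6 tests and about 20% to 24%.

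What remains is that the SAP chooses none of these options and leaves baseline adjustment unused.

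**Conclusion.** The point holds as a gap in prespecification with an inexpensive improvement, of low severity. The plan fixes no visit, contrast or baseline adjustment for ESR and hsCRP, and its wording is consistent with a chance of a false positive from about 9% (2 tests) to about 28% to 41% (12 tests). The upper figure requires all six form visits to follow randomisation and all of them to be tested. Adjusting for baseline reduces the SE at one visit by 8% to 19% or by 5% to 29%, depending on whether the SAP's test would be applied to change scores or to raw values. All these sizes rest on assumed correlations, since the documents give none.

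The markers are outside the numbered secondary endpoints. The primary conclusion rests on a confidence interval for a difference in response proportions, so nothing here alters it.

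**What to change.** Add a short paragraph to the SAP, before the data are seen:

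- For ESR and for log hsCRP, estimate one LEF minus SSZ contrast with a 95% CI, with the value at randomisation as covariate. ANCOVA at one visit, or a repeated-measures mixed model (arm, visit, arm by visit) on all observed monthly readings, would each serve.
- Name the time point or averaging window. Week 12 would match the primary endpoint. An average over visits is also legitimate if it is described as such. The choice is one of preference, but it must be made in advance.
- State that the baseline is the reading at randomisation, not at the start of methotrexate, and that the form's week columns count from randomisation, if that is what is intended.
- Report the other visits descriptively, without p-values.
- Say whether the two contrasts are supportive only (about 9% family-wise error) or are tested at 0.025 each, which holds the family at 5% or less.

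The mixed model uses observed readings and needs no carry-forward for these markers. Whether carry-forward should stay elsewhere in the SAP is a separate question.

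The cost is a few lines of SAP text and slightly more analysis work. The readings are already scheduled, so there is no extra visit, sample or patient.
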